7.1.2 Neuropsychological testing and Questionnaires

The risks posed by neuropsychological testing are temporary fatigue and mild frustration.

Fatigue. Participants will be reminded that they are free to take a break if feeling tired.

Frustration. If the participant appears to be excessively frustrated, they may discontinue that test and be offered an easier one. If a participant is unwilling to continue a testing session, they will be given the option of continuing at a later time, ending the current session, or ending all participation.

7.1.3 Blood draws for analysis of biomarkers and genetics

Blood draw discomforts. There is a small risk of pain with a blood draw when the needle enters the skin. Bruising at the site of the needle stick may occur, but this is temporary. Some people may experience fainting or dizziness. To minimize these risks, experienced personnel at the VA Outpatient Surgical Center will handle all the blood drawing procedures.

Blood draw infection risk. Sterile conditions are maintained at the VA Outpatient Surgical Center. In the unlikely event of infection at the site of the needle stick, the participant will be treated at the study site.

Genetic testing concerns. It is possible that biomarker and genetic testing could cause some psychological stress in a few individuals. All participants will be informed that tissue samples and results of the biomarker and genetic testing will be labeled using a code that has no individual identification. Participants will be informed that we will not release

results of the genetic testing to them, to members of their family, physician, or other third party.

7.1.4 rTMS

TMS Safety Screening (Telephone pre-screen and Visit 1 in-person screen)

To minimize risks and AEs related to rTMS, the same ferromagnetic safety policies and procedures described above for MRI will be applied to rTMS safety screening. During the consenting and history taking process, we emphasize to participants that giving false information about their medical history, including past and present drug use, could have serious consequences for their health and well-being.

Individuals who might be prone to seizures (e.g. have had a recent traumatic brain injury, have history of a seizure disorder, need to be on medications that substantially increase the risk of having seizures, or abuse medications or use illegal substances that can increase the chance of having a seizure) will be excluded from this study, as documented on the Medical History and the Inclusion/Exclusion Forms.

Even though psychotic symptoms and suicidal ideation have been never described in normal subjects during or after rTMS, there is a report of one patient with major depressive disorder who developed delusions during rTMS treatment (Zwanzger, Ella, Keck, Rupprecht, & Padberg, 2002). In the present MCI rTMS study, participants with a Geriatric Depression Scale score ≥ 6 will not be eligible to enroll. (They will be referred for evaluation and treatment of their depressive symptoms.)

Safety and AE Monitoring during the rTMS Study Treatment Sessions 1-20

Eligible participants will be closely monitored by the study physician and the certified TMS operator during the intervention phase to minimize the risks associated with the rTMS intervention/device and to document adverse effects.

At the beginning of every morning treatment session, the participant will be asked about changes in mental and physical health, sleep patterns, changes in prescribed medications, recent alcohol consumption, and recent use of non-prescribed drugs, using the TMS Session Safety Questionnaire. This questionnaire will be used by the TMS Operator to probe an AE further. All AEs will be documented on the Adverse Event form.

In case of a safety concern, the Study Coordinator or TMS Operator will alert the Study Physician before proceeding with rTMS. If the participant reports having had less than one hour of sleep the previous night, the rTMS session will be postponed until the participant's sleep pattern improves. During every session, the rTMS Operator will monitor the participant's ear protection, coil placement, and possible seizure activity. The log sheet explicitly reminds the Operator to notify the Study Physician in the event of a change in medication, change in sleep pattern, recent consumption of more than 1 alcoholic beverage, or use of street drug. Motor thresholds (MTs) will be rechecked at the Study Physician's direction. Rechecked MTs and power outputs will be documented in the participant's intervention log.

If an AE occurs: Risk management, modifications, and assessments

Discomfort. Should a headache or site discomfort occur, these symptoms are expected to be self-treated (e.g. with ibuprofen). Reported levels of discomfort often diminish in later sessions in the absence of over the counter (OTC) pain medications. If dental pain occurs,

study staff may be able to move the rTMS coil position slightly or provide a bite block to reduce or prevent the pain.

Ear Protection. To protect against possible hearing damage, participants will wear ear protection during rTMS sessions.

Syncope. Occasionally, syncope occurs with TMS, particularly in initial sessions. Staff will provide reassurance and monitor the participant for level of anxiety and psycho-physical discomfort. Premonitory complaints are: "I need to lie down", or "I need air" "I think I'm going to black out." Visceral distress, nausea, dizziness, pallor, and diaphoresis are other symptoms. Upward eye deviation, which is common in circulatory syncope, is rare in partial seizures unless there is progression to generalized convulsions. Because participants will be reclined in a chair during the stimulation procedure, the risk of syncope and a fall-related injury are lower. Study staff will be trained to be first responders to these unlikely events, and will know to call the VAPAHCS facility's E-Team as a proactive measure. Uncomplicated syncope *not* requiring hospitalization is normally considered an adverse event; the seriousness of the AE is a clinical judgement of the study physician.

Seizure. The VAPAHCS facility where the rTMS treatment sessions are performed is fully equipped to safely handle a seizure. The initial management of syncope and seizure is identical. Clinically, the cardinal feature that distinguishes syncope from seizure is rapid recovery of consciousness within seconds and not minutes. Delayed recovery of normal consciousness beyond 30 seconds mandates further evaluation and a neurological work-up. The participant will be treated at the study site for any medical or psychological consequences. Procedures for medical care, for documenting this study-specific SAE, and for monitoring the outcome of a seizure-related SAE are described separately in seizure safety protocol (see Appendix VI. "Seizure Protocol").

7.2 Summary of Safety Assessments

Safety will be measured based on the occurrence of serious adverse events, such as seizures, and syncope that results in hospitalization. Tolerability of rTMS will be based on the number of adverse events reported (grouped per side effect type) and number of dropouts due to AEs and other reasons during the intervention phase of the study.

All AEs will be documented on the Adverse Event form. If the AE is serious, then the SAE will be further documented on the SAE Form. Briefly, the forms contain the event description, severity, outcome, recovery date, and other follow-up information.

7.3 Adverse Events and Serious Adverse Events

Definitions for Adverse Events (AEs)

An **Adverse Event (AE)** is any untoward medical occurrence, including any abnormal sign, symptom, or disease *temporally* associated with study participation, whether or not considered related to participation in the research.

- An AE is deemed to be associated with the use of the study device if there is "a reasonable possibility that the experience may have been caused by the device."
- Chronic problems which are unchanged from baseline are not considered AEs. However, worsening of an ongoing condition would be considered an AE.

A **Serious Adverse Event (SAE)** is an adverse event that

- results in death

- is life-threatening, or places the participant at immediate risk of death from the event as it occurred
- requires or prolongs hospitalization
- leads to persistent or significant disability or incapacity
- is a seizure (Note: intervention-specific SAE definition)
- Is another condition which investigators judge to represent significant hazards.

An **Unanticipated Adverse Device Effect (UADE)** is an SAE caused by or associated with a device, if that effect, problem, or death was not previously identified in nature, severity, or degree of incidence, or any other unanticipated serious problem associated with a device that relates to the rights, safety, or welfare of patients.

Time span of collecting AEs and SAEs

Collection of all adverse events will begin at the time the participant signs the informed consent form and will continue throughout the 6-month post-intervention follow-up phase:

- At the Baseline visit, the participant and study partner (SP) will be asked about changes in medications, any other health or behavior changes, and any medical care received since the Screening visit;
- At each Intervention session, the participant will be asked about any side effects experienced. At each morning Intervention session, the participant will additionally be asked about any changes in medications, any other health or behavior changes, and any medical care received;
- At the Immediate Post-Intervention Follow-up visit, the participant will be asked about any side effects experienced since last seen, and any changes in medications, any or other health or behavior changes since the previous visit or phone follow-up, and any medical care received;
- At the 3- and 6-Month Follow-up visits, the participant will be asked about any changes in medications, medical care received, or other health or behavior changes since the previous visit or phone follow-up.

In summary, study staff will screen for new AEs/SAEs and review any unresolved AEs/SAEs at each encounter with the participant.

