6.1 Schedule of Assessments

On the following page, **Table 2** lists the study assessments and their timing during the Pre-Treatment, Treatment, and Follow-up phases of the study. Following Table 2, we list each assessment that will be performed during these phases.

Table 2. Schedule of Assessments

	Pre-Treatment Phase		Treatment Phase			Follow-up Phase		
Visit Description	In-person Screening	Randomization & Baseline	Sessions 1-10	Sessions 11-20	Make-up sessions allowed through Day 37	Immediate Post-Tx	3-Month Post-Tx	6-Month Post-Tx
Visit Number	1	2	3-7	8-12		13	14	15
Timeline	Days -42 to -35	Day 0	Days 7-11	Days 14-18	Days 21-37	7 ± 3 days after S20	90 ± 14 days after S20	180 ± 14 days after S20
Informed Consent Form	X							
Demographics	X							
Vital Signs	X		X	X	X		X	X
Cognitive Change Index; MMSE, Logical Memory I	X							
CDR (Subject and SP)	X							
GDS, ETOH Questionnaire, Logical Memory II	X							
Medical, Psychiatric & Seizure Hx; Hach; PE/NE; Diagnostic Summary	X							
Concomitant Medications	X	X	X	X	X	X	X	X
MRI and rTMS Safety forms; Motor Threshold (MT)	Safety & Left MT	Safety	Safety & Right MT	Safety	Safety	Safety		
Inclusion/Exclusion Criteria	X							
Enrollment/Randomization		X						
MRI scan		X				X		
CVLT-II and Secondary Behavioral Assessments		X				X	X	X
Blood Sample (Genomic DNA and BDNF Biomarkers)			Session 1 DNA & BDNF		Session 20 BDNF only			
rTMS Intervention Log			X	X	X	X	X	
Adverse Events		X	X	X	X	X	X	X

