6.2.4 Follow-up Visits (Visits 13, 14 and 15)

Immediate Post-Treatment (Visit 13)

The Immediate Post-Treatment Visit 13 needs to occur 7 ± 3 days after the 20th and final intervention session.

- Each of the assessments and procedures performed at the Baseline Visit will be repeated at this visit. See Section 6.2.2.

- In addition, the participant and study partner will be asked to complete a brief questionnaire regarding their views on the acceptability of rTMS as a treatment.

Follow-up at 3-Month (Visit 14)

Visit 14 can be completed ± 2 weeks of the target date.

- Vital Signs
- Concomitant Medications
- Adverse Events
- Cognitive Assessment Battery, administered by the Study Coordinator
- ECog and FAQ Functional Outcome Questionnaires completed by Participant and/or Study Partner

6-Month Follow-up (Visit 15)

Visit 15 can be completed ± 2 weeks of the target date.

- Each of the assessments performed at the 3-Month Follow-up will be repeated.
- The Study Completion/Participant Withdrawal Form will be filled out to document the participant's completion of the study.

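### At the 3- and 6-month visits Section 7.3 names only the memory-impaired participant as adverse-event informant, over nominal recall gaps of 83 and 90 days; the study partner should be named too

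*Combined protocol and SAP*

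**What the plan says.** Section 7.3 (time span of collecting AEs and SAEs) sets out visit by visit who is asked.

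- Baseline: "At the Baseline visit, the participant and study partner (SP) will be asked about changes in medications", together with other health changes and medical care since Screening.
- Immediate post-treatment (Visit 13): "At the Immediate Post-Intervention Follow-up visit, the participant will be asked about any side effects experienced since last seen". Only the participant is named.
- Visits 14 and 15: "At the 3- and 6-Month Follow-up visits, the participant will be asked about any changes in medications, medical care received", and other health or behavior changes. Again only the participant is named.

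Section 6.2.4 lists adverse events as an item at Visit 14 and does not say who is asked. Visit 15 follows suit: "Each of the assessments performed at the 3-Month Follow-up will be repeated".

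The partner has a role throughout. Section 4.1 makes an available study partner an inclusion criterion, alongside a diagnosis of amnestic MCI. Section 6.2.3 has the rTMS Safety Questionnaire completed by the participant together with the partner. At Visit 14 the list includes "ECog and FAQ Functional Outcome Questionnaires completed by Participant and/or Study Partner", and Section 6.2.2 assigns the FAQ to the partner.

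Table 2 (Section 6.1) places Visit 13 at "7 ± 3 days after S20", Visit 14 at "90 ± 14 days after S20" and Visit 15 at "180 ± 14 days after S20".

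**The concern.** The partner is written in as a safety informant where recall is short and left out where it is longest. At Visits 14 and 15 the stated rule asks people selected for poor episodic memory to reconstruct about three months of health events, medication changes and medical care.

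Two uses of the data are exposed. Section 9.5.2 summarizes adverse events by treatment group and by study phase, with follow-up as its own phase, and allows t-tests or chi-square tests. Section 7.4 requires SAEs to reach the DSMB and the NIA within 24 hours of staff learning of them, so a hospitalization that nobody mentions never starts that clock. The primary efficacy analysis is not affected.

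**Working it through.** **1. Recall gaps from Table 2.** All days are counted from Session 20.

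- Visit 13: 7 ± 3, so days 4 to 10.
- Visit 14: 90 ± 14, so days 76 to 104.
- Visit 15: 180 ± 14, so days 166 to 194.

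Nominal gap = difference of target days. Shortest gap = earliest later visit minus latest earlier visit. Longest gap = latest later visit minus earliest earlier visit.

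| Interval | Nominal | Shortest | Longest |
|---|---|---|---|
| Visit 13 to 14 | 90 − 7 = 83 days (11.9 weeks) | 76 − 10 = 66 days | 104 − 4 = 100 days (14.3 weeks) |
| Visit 14 to 15 | 180 − 90 = 90 days (12.9 weeks) | 166 − 104 = 62 days | 194 − 76 = 118 days (16.9 weeks) |

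For comparison, the treatment visits in Table 2 fall on Days 7–11 and 14–18, so the longest scheduled gap between them is 14 − 11 = 3 days. That is the phase with the partner-assisted questionnaire.

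**2. Whether anything else fills the gaps.** Table 2 shows no contact between Visits 13, 14 and 15. Its safety-form row ends at Visit 13, and Section 6.2.4 lists no safety questionnaire at Visits 14 or 15. Section 7.3 mentions a phone follow-up, but the calls that are described serve particular cases: withdrawal because of an SAE or UADE, or a seizure (6.2.5), permanent discontinuation (8.1), temporary discontinuation (8.2), and withdrawal with an ongoing event (8.3). A participant who completes treatment without problems gets none.

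**3. Whether another section restores the partner.** For Visits 14 and 15, none does. Visit 13 differs: Section 6.2.4 repeats every Baseline assessment and procedure there. Baseline includes adverse-event monitoring, which Section 7.3 puts to participant and partner. Visit 13 also comes only 4 to 10 days after Session 20. It therefore needs its wording reconciled and is not a long-recall problem.

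**4. Possible size, on assumptions only.** The plan gives neither a follow-up event rate nor a recall rate. Let p be the true proportion with an event and s the proportion of those detected, equal in all arms. Participants with a missed event per arm of 33 = 33 × p × (1 − s).

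- p = 20%, s = 90%: 33 × 0.20 × 0.10 = 0.7.
- p = 40%, s = 70%: 33 × 0.40 × 0.30 = 4.0.
- p = 60%, s = 50%: 33 × 0.60 × 0.50 = 9.9.

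With equal detection and equal true rates, no false difference between arms arises. If detection in one arm were 10 to 20 points higher, the false difference would be p times that gap: from 0.20 × 10 = 2 points to 0.60 × 20 = 12 points. These ranges show only how the answer depends on unknown inputs; they are not estimates.

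**The case against.** The strongest reply is that naming the participant does not exclude the partner. Section 7.3 uses the same participant-only wording for treatment sessions, yet Section 6.2.3 has the partner help with the Safety Questionnaire and expects reports from either person. A reader might infer that follow-up reports must come from the participant alone. The documents do not say so: nothing forbids asking the partner. Section 11.2 also refers to a partner consent form describing what the partner will be asked to provide, and that form and the visit forms were not available for this review. This part of the objection stands. Even so, during treatment a second section brings the partner in, whereas for Visits 14 and 15 none does. Staff who follow the text would ask the participant.

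The consequence can also be overstated. rTMS has ended by then, so this is post-treatment observation time, not exposure. Section 7.2 rests safety on serious events and takes dropouts during the intervention phase as a measure of tolerability. Impairment is mild (overall CDR 0.5 in Section 6.2.2; an MMSE below 24 is a screen failure in Section 11.2). The medication review and the question about medical care prompt recall. All of this limits the harm without removing it.

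A reader might further infer that follow-up safety comparisons are biased whenever rTMS works, because better memory would mean more events reported in the active arms. That requires a gain on a word-list test to carry over to recall of medical events and to last. The working hypothesis in Section 9.1 is an effect sustained only up to 3 months, and no figure in the documents gives a size or direction. Blinded staff would not remove such an effect, so it remains possible, but no more.

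**Conclusion.** The point holds for Visits 14 and 15. The stated rule relies on participants with amnestic MCI to recall nominally 83 and 90 days (at most 100 and 118 within the windows), while a required partner who is already supplying data is not named. Under-reporting of post-treatment events in the follow-up summary is likely; this is an inference from the population and the gaps, not a documented fact. It assumes that staff ask whom Section 7.3 names and that partners would recall some events that participants do not. How many events would be lost cannot be determined from the documents, and unequal loss by arm is only a possibility. This is a worthwhile, low-cost improvement to safety ascertainment, not a flaw in the efficacy design.

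**What to change.** In Section 7.3, name the participant and the study partner as informants at Visits 14 and 15, using the form already written for Baseline. Say the same beside the adverse-event item in Section 6.2.4. Ask the partner in person, or by phone, when the ECog and FAQ are collected. The and/or wording there means that a partner may not be present, so the phone route should be explicit. Add a field to the adverse-event form for the source: participant, partner or both. For Visit 13, only reconcile Section 7.3 with Section 6.2.4, which already repeats the Baseline procedures. Check that the partner consent form covers this reporting.

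The cost is a wording change, one form field and a few minutes per visit, with no new visit or staff. A few more minor events will be recorded. Two informants may report the same event, but Section 7.4 already makes the principal investigator responsible for preventing double capture.

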7.4 Reporting Procedures

Time lines for reporting AEs and SAEs

The PI and research team will notify the DSMB and the NIA Program Official of all SAEs (regardless of intervention vs. follow-up phase) by group email within 24 hours of study staff's knowledge of the event.

- The emailed, expedited report will be followed by a detailed, written initial SAE report as soon as possible.
- The PI is responsible for verifying that the report has been submitted and that the DSMB Chair and NIA Program Official acknowledge receipt.

The PI and research team will report SAEs to the local IRB per Stanford University's HRPP Policy Guidance "Events and Information that Require Prompt Reporting to the IRB" GUI-P13 1/3 (see Appendix X).

All adverse events will be reported annually or more often to the DSMB, Stanford IRB, and NIA staff.

- The study's Data Manager will generate tabulations of all AEs (including SAEs and non-serious AEs) and present a summary of these to the DSMB and NIA staff on a schedule set by the DSMB.
- Aggregate summaries of SAEs and non-serious AEs will also be reported annually to the Stanford IRB.

Procedures and forms for recording AEs

Any new condition, recurrence of a previously resolved condition, or worsening of a pre-existing condition will be reported as an AE. (The Screening Visit Medical History Form provides a list of all pre-existing conditions and whether each condition is resolved or ongoing.)

All adverse events (including adverse device effects) will be recorded on the AE report form (based on NIH Template AE form 9a) and, if severe, on the SAE form (based on NIH Template SAE form 9b). Both SAEs and UADEs will be recorded using SAE form 9b. All adverse events will be assessed as "Not related," "Possibly related," or "Definitely Related" to the intervention or to other study procedures.

Decisions regarding AE relatedness and severity

The Study Physician will be responsible for decisions regarding relatedness and severity.

Assessment of study relatedness. Relatedness involves an assessment of the degree of causality between the study intervention and the event. Relatedness can be assessed by considering the following criteria:

- Previously reported with this treatment,
- Occurred after treatment began,
- Improved when treatment is withdrawn or a specific antagonist administered,
- Reappearance upon re-challenge,
- No alternative causes for the reaction,
- Increased severity when dose increased or lessened when dose decreased,
- Patient previously had similar reaction when exposed to the treatment, and
- Reaction confirmed by objective evidence.

Study-relatedness criteria.

- All adverse events or effects with a clear causal relationship to the intervention or to the procedures involved in the research should be considered "**Definitely related**".
- All adverse events or effects with a possible causal relationship to the intervention or to the procedures involved in the research should be considered "**Possibly related**".
- In general, if event is determined to be caused solely by an underlying disease, disorder, or condition of the subject, or due to other circumstances unrelated to either the research or any underlying disease, disorder, or condition of the subject, it would be considered "**Unrelated**" to participation in the research.

Study Staff Responsibilities

- During the pre- and post-intervention phase of the study, the Study Coordinator will be responsible for collection of initial AEs, follow-up of AEs (see Section 7.5) and completion of AE forms.
- The TMS Operator will be responsible for initial AE collection, follow-up, and form completion during the intervention phase.
- The Study Physician will be responsible for reviewing all AEs and for making decisions regarding relatedness and severity.
- The PI will be responsible for reviewing the AE forms for completeness and accuracy, for monitoring the AE data to avoid double capture of AEs, and for monitoring charts and CRFs for documentation of the physician's review of AEs.

